**Figure JAIN.5.1.**

**Illustration of study design for Clinical Protocol I4V-MC-JAIN.**

## 5.1. Method of Assignment to Treatment

**At Week 0 (Visit 2),** patients who meet all criteria for enrollment will be randomized in a 1:1:2:1 ratio to receive double-blind treatment with placebo QD, baricitinib 1-mg QD, 2-mg QD, or 4-mg QD. Randomization will be stratified by geographic region and disease severity at baseline (IGA 3 vs 4). Assignment to treatment groups will be determined by a computer-generated random sequence using an interactive web-response system (IWRS). The IWRS will be used to assign cartons, each containing 4 blister packs of double-blind investigational product tablets to each patient, starting at Visit 2 (Week 0), and at each visit up to and including Visit 27 (Week 184). Site personnel will confirm that they have located the correct carton by entering a confirmation number found on the carton into the IWRS.

This study will be conducted internationally at multiple sites.

Table JAIN.5.1 below describes how regions will be defined for stratification. Regions may be combined for statistical analyses when one of the region strata fails to meet the minimum number of patients. Details are provided in Section 6.2.2.2.

**Table JAIN.5.1. Geographic Regions for Stratification**

Region	Country
Europe (EU)	Austria, Belgium, Finland, France, Germany, Italy, Netherlands, Poland, Spain, Switzerland, UK
Japan (JP)	Japan
Rest of World (ROW)	Brazil, Russia

**In Period 3** (Week 52 [Visit 14] to Week 104 [Visit 22]), eligible patients may be re-randomized depending on their response to treatment. Re-randomization for the Down-Titration Substudy (at Week 52 [Visit 14]) is stratified by IGA (0 or 1 vs 2).

**In Period 4** (Week 104[Visit 22] to Week 200[Visit 28]), patients will continue to receive the same treatment (baricitinib or placebo) they received during Period 3 and will have the same options for dose change as Period 3 (if not already implemented in Period 3).

## 6. A Priori Statistical Methods

### 6.1. Determination of Sample Size

Study JAIN will aim to enroll 500 patients  $\geq 18$  years of age. Ignoring stratification, the proposed sample size will ensure  $>90\%$  power based on the Chi-square test to detect an absolute difference of approximately 25% between the 4-mg baricitinib and the placebo treatment group and the 2-mg baricitinib and placebo treatment group, each using a 2-sided alpha of 0.025 and assuming approximately 20% placebo response rate for the primary endpoint. These assumptions are based on what was observed in Phase 3 Study 14V-MC-JAIY.

Sample size and power estimates were obtained from nQuery® Advisor 7.0.

### 6.2. General Considerations

This plan describes a priori statistical analyses to be performed for efficacy, health outcomes, and safety.

Statistical analysis of this study will be the responsibility of Eli Lilly and Company (Lilly). The statistical analyses will be performed using SAS® Version 9.4 or higher.

Not all displays described in this SAP will necessarily be included in the clinical study report (CSR). Not all displays will necessarily be created as a “static” display. Some may be incorporated into interactive display tools instead of or in addition to a static display. Any display described in this SAP and not included in the CSR are available upon request.

Statistical tests of treatment effects and confidence intervals (CIs) will be performed at a 2-sided significance level of 0.05, unless otherwise stated (for example, graphical multiple testing strategy in Section 6.4).

Data collected at ETVs will be mapped to the closest scheduled visit number for that patient if it falls within the visit window discussed in Section 6.2.2. For by-visit summaries, only visits in which a measure was scheduled to be collected will be summarized.

Any unscheduled visit data will be included in the patient-level listings. However, the data will still be used in other analyses, including shift analyses for safety analytes, change from baseline to endpoint using modified last observation carried forward (mLOCF) for efficacy analyses, and other categorical analyses including safety.

Although Period 3 goes through Week 104 (Visit 22) and Period 4 goes through Week 200, daily diary collection only continues through Week 68 (16 weeks after Week 52; Visit 18).

#### 6.2.1. Analysis Populations

The following major analysis populations will be used in SAP for the analysis (additional analysis populations for specific analysis will be defined in the corresponding analysis section):

**Intent-to-treat (ITT) population:** The ITT population analysis set is defined as all randomized patients..

**Per-protocol Set (PPS):** The PPS of the ITT population analysis set will include those patients who are not deemed noncompliant with treatment in Period 2 (up to Week 52), who do not have significant protocol violations, and whose investigator site does not have significant good clinical practice (GCP) issues that require a report to the regulatory agencies prior to Week 16 (Visit 8). Qualifications for and identification of significant protocol deviations will be determined while the study remains blinded, prior to DBL. Details can be found in Section [6.15](#).

Unless otherwise specified, the efficacy and health outcome analyses for Period 2 will be conducted on the ITT population (Gillings and Koch 1991), which seeks to preserve the benefits of randomization and avoids the issue of selection bias. Patients will be analyzed according to the treatment to which they were assigned, even if the patient does not receive the correct treatment, or otherwise did not follow the protocol. In addition, the primary and key secondary analyses will be repeated using the PPS population.

**Safety population:** The safety population is defined as all randomized patients at Visit 2 who receive at least 1 dose of investigational product and who did not discontinue from the study for the reason 'Lost to Follow-up' at the first postbaseline visit. This definition excludes patients with no safety assessments postbaseline so that incidence rates are not underestimated.

Safety analyses will be done using the safety population. Patients will be analyzed according to the treatment regimen to which they were assigned. Analyses of the safety endpoints, many of which are incidence based, will include all patients in the safety population, unless specifically stated otherwise. In the rare situation where a patient is lost to follow-up at the first postbaseline visit but some safety data exist (for example, unscheduled laboratory assessments) after first dose of study drug, a listing of the data or a patient profile will be provided when requested.

The time period for safety analysis of the 24-week interim analysis will be following criteria whichever occurs first:

- up to last dose plus up to 30 days in the study
- the first dose in Period 3
- up to dose change or up to the data cutoff date

The time period for safety analysis of the 52-week interim analysis will be following criteria whichever occurs first:

- up to last dose plus up to 30 days in the study
- the study discontinuation date
- up to dose change
- the first dose date in Period 3

**The time period for safety analysis of the 104 interim analysis** will be following criteria whichever occurs first:

- up to last dose plus up to 30 days in the study
- the study discontinuation date
- up to dose change date due to rescue

- up to dose change date due to retreatment
- the first dose in Period 4
- up to the data cutoff date

**The time period for safety analysis of the final analysis** will be following criteria whichever occurs first:

- up to last dose plus 30 days or up to last date in the study
- the study discontinuation date
- up to dose change

**Long-Term Extension (LTE) Substudy Population:** The LTE Substudy Population is defined as the patients who received at least one study medication in Period 3 of Study JAIN, and entered the downtitration substudy. Additionally, those patients who did not met study discontinuation criteria in Period 3 and continued in Period 4 will be considered in the analysis set.

**Long-Term Extension(LTE) Substudy Relapse Population:** for a subset of patients in the LTE Substudy Population defined as above who experienced a relapse in Period 3 or Period 4 (IGA $\geq$ 3 after Week 52).

**Long-Term Extension(LTE) Non-responder Population:** The LTE Non-responder Population is defined as the patients who received at least one study medication in Period 3 of Study JAIN, and IGA $\geq$ 3 at Week 52. Additionally, those patients who did not met study discontinuation criteria in Period 3 and continued in Period 4 will be considered in the analysis set.

**Long-Term Extension(LTE) Responders & Partial Responders who did not enter the Substudy:** This population is defined as the patients who received at least one study medication in Period 3 of Study JAIN, and were Responders (IGA 0 or 1) and Partial Responders (IGA 2) at Week 52 but were not eligible for downtitration substudy (i.e. had study drug interrupted at Week 52, or had received high or ultra-high potency TCS in the previous 14 days). Additionally, those patients who did not met study discontinuation criteria in Period 3 and continued in Period 4 will be considered in the analysis set.

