### **6.2.2. General Considerations for Analyses for the 24-Week, 52-Week, , 104-Week Interim Analysis, and Final DBL**

**Period 2** starts at randomization (Visit 2, Week 0) and ends with the visit at Week 52 (Visit 14) or the early discontinuation visit (between Weeks 0 and 52).

**24-week interim analysis** will be done when all the patients complete Week 24 assessment (Visit 10) or discontinue study or treatment before the Week 24 assessment.

**52-week interim analysis** will be done when all the patients complete Week 52 assessment (Visit 14) or the early termination visit (between Weeks 0 and 52).

**Period 3** starts at re-randomization (Visit 14, Week 52) and ends with the visit at Week 104 (Visit 22) or the early discontinuation visit (between Weeks 52 and 104).

**104-week interim analysis** will be conducted when all the patients complete Week 104 assessment (Visit 22) or the early termination visit (between Weeks 0 and 104).

**Period 4** starts at (Visit 22, Week 104) and ends with the visit at Week 200 (Visit 28) or the early termination visit (between Weeks 104 and 200). For the final DBL, efficacy endpoints beyond week 104 will be exploratory in nature and will be analyzed in a descriptive way using observed data.

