## 6.7. Treatment Compliance

**For 24-week interim analysis**, patient compliance with study medication will be assessed for the following:

- Week 0 (Visit 2) through Week 16 (Visit 8) or Early Termination using the ITT population.
- Week 0 (Visit 2) through Week 24 (Visit 10) or Early Termination using the ITT population.

**For 52-week interim analysis**, patient compliance with study medication will be assessed for the following:

- Week 0 (Visit 2) through Week 52 (Visit 14) or Early Termination using the ITT population.

**For 104-week interim analysis**, patient compliance with study medication will be assessed for the following:

- Week 52 (Visit 14) through Week 104 (Visit 22) or Early Termination using the Long-Term Extension Substudy Population, and the Long-Term Extension Non-responder Population.

**For Final analysis**, patient compliance with study medication will be assessed for the following:

- Week 52 (Visit 14) through Week 200 (Visit 28) or Early Termination using the LTE Substudy Population, the LTE Non-responder Population & LTE responders/partial responders who did not enter the Substudy

All patients are expected to take 3 tablets daily from a blister pack as described in the protocol. Each blister pack contains 27 tablets. A patient is considered noncompliant if he or she misses >20% of the prescribed doses during the study, unless the patient’s study drug is withheld by the investigator. For patients who had their treatment temporarily interrupted by the investigator, the period of time that dose was withheld will be taken into account in the compliance calculation.

Compliance in the period of interest up to Visit  $x$  will be calculated as follows:

$$\text{Compliance} = \frac{\text{total number of tablets dispensed} - \text{total number of tablets returned}}{\text{expected number of total tablets}}$$

where

- Total number of tablets dispensed: sum of tablets dispensed in the period of interest prior to Visit  $x$ ;
- Total number of tablets returned: sum of the tablets returned in the period of interest prior to and including Visit  $x$ ;
- Expected number of tablets: number of days in the period of interest\*number of tablets taken per day = [(date of visit – date of first dose + 1) – number of days of temporary drug interruption]\*number of tablets taken per day

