A patient will be considered significantly noncompliant if he or she misses more than 20% of the prescribed doses of investigational product during the study, unless the patient's investigational product is withheld by the investigator for safety reasons. Similarly, a patient will be considered significantly noncompliant if he or she is judged by the investigator to have intentionally or repeatedly taken 20% more than the prescribed amount of investigational product during the study. Patients who are significantly noncompliant through Week 16 will be excluded from the PPS population.

Descriptive statistics for percent compliance and noncompliance rate will be summarized for the ITT population by treatment group for Week 0 through Week 16 and Week 0 through Week 24 and Week 0 through 52. Subintervals of interest, such as compliance between visits, may also be presented. The number of expected doses, tablets dispensed, tablets returned, and percent compliance will be listed by patient for Week 0 through Week 16, Week 0 through Week 24, and Week 0 through Week 52. Additionally, treatment compliance will be summarized for the LTE Substudy Population, the LTE Non-responder Population & LTE responders/partial responders who did not enter the Substudy populations from Week 52 through Week 200.

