## 6.15. Protocol Deviations

Protocol deviations will be tracked by the clinical team, and their importance will be assessed by key team members during protocol deviation review meetings. Of all the important protocol deviations (IPDs) identified, a subset occurring during Treatment Period 2 with the potential to affect efficacy analyses will result in exclusion from the PPS population.

Potential examples of deviations include patients who receive excluded concomitant therapy, significant non-compliance with study medication (<80% of assigned doses taken, failure to take study medication and taking incorrect study medication), patients incorrectly enrolled in the study, and patients whose data are questionable due to significant site quality or compliance issues.

The Trial Issue Management Plan includes the categories and subcategories of IPDs and whether these deviations will result in the exclusion of patients from the PPS.

The number and percentage of patients having IPD(s) will be summarized within category and subcategory of deviation by treatment group for Treatment Period 2 using the ITT population.

Individual patient listings of IPDs will be provided. A summary of reasons patients were excluded from the PPS will be provided by treatment group.

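### The per-protocol set has two conflicting compliance windows (Week 52 in SAP 6.2.1, Week 16 in SAP 6.7), and the longer one does not fit analyses that all fall at Week 24 or earlier

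*SAP*

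**What the plan says.** Three places in the SAP decide who is in the PPS.

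- Section 6.2.1 (Analysis Populations) includes "those patients who are not deemed noncompliant with treatment in Period 2 (up to Week 52"). It adds two more conditions, one on violations of the protocol and one on the site. The site condition reads "whose investigator site does not have significant good clinical practice (GCP) issues that require a report to the regulatory agencies prior to Week 16 (Visit"; the visit named there is Visit 8.
- Section 6.7 (Treatment Compliance) says: "Patients who are significantly noncompliant through Week 16 will be excluded from the PPS population".
- Section 6.15 (Protocol Deviations) says that, of the important deviations, "a subset occurring during Treatment Period 2 with the potential to affect efficacy analyses will result in exclusion from the PPS population". Its examples include "significant non-compliance with study medication (<80% of assigned doses taken").

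Section 6.2.1 also says that the primary and key secondary analyses will be repeated in the PPS. Tables JAIN.6.8 and JAIN.6.11 place those repeats at Weeks 1, 2, 4, 16 and 24. None is at Week 52, and each is labelled a sensitivity analysis.

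On timing, Section 6.2.2 says that the 24-week interim analysis "will be done when all the patients complete Week 24 assessment (Visit 10") or have discontinued. Protocol 10.3.1.3 makes this the primary analysis for submission. The longest compliance window that Section 6.7 plans for that lock is "Week 0 (Visit 2) through Week 24 (Visit 10) or Early Termination using the ITT population". Compliance over Weeks 0 to 52 is first planned for the 52-week lock.

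**The concern.** One analysis set has two stated compliance windows, and Section 6.15 sides with the longer one. Two programmers who both follow the SAP could build different sets and report different PPS results for the primary and key secondary endpoints.

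The Week 52 window also does not suit the analyses that use it. What goes wrong depends on when the set is built:

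- **At the 24-week lock**, Week 52 compliance is incomplete for every patient still in Period 2, so the 6.2.1 rule cannot be applied in full.
- **At a later lock**, inclusion in a Week 16 analysis would depend on tablets missed or deviations made after Week 16. Later adherence can itself be influenced by response or tolerability, so the set would be selected on something that follows the endpoint.

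At stake is whether a reader can tell which patients the PPS sensitivity analyses contain, and whether those analyses condition only on events up to the endpoint.

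**Working it through.** The plan states no figure for the size of the PPS, so there is none to reproduce. The check is whether the two windows can classify the same patient differently.

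**Inputs**

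- Daily dose count: "All patients are expected to take 3 tablets daily from a blister pack as described in the protocol" (SAP 6.7).
- Threshold: noncompliant if more than 20% of doses are missed, that is, below 80% (SAP 6.7 and 6.15).
- Formula (SAP 6.7): compliance = (tablets dispensed − tablets returned) / expected tablets, where expected tablets = (days in period − days interrupted) × 3. This is cumulative over the period.
- Windows, assuming no interruptions: Week 16 = 16 × 7 = 112 days, 336 tablets; Week 24 = 168 days, 504 tablets; Week 52 = 364 days, 1,092 tablets.

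**Patient A: 100% to Week 16, then 70%**

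- Week 16 compliance is 100%: in the PPS under 6.7.
- Week 52 compliance = (112 × 1.00 + 252 × 0.70) / 364 = 288.4 / 364 = 79.2%: out under 6.2.1.
- Break-even after Week 16 = (0.80 × 364 − 112) / 252 = 179.2 / 252 = 71.1%.

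**Patient B: 70% to Week 16, then 85%**

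- Week 16 compliance is 70%: out under 6.7.
- Week 52 compliance = (112 × 0.70 + 252 × 0.85) / 364 = 292.6 / 364 = 80.4%: in under 6.2.1.
- Break-even after Week 16 = (291.2 − 78.4) / 252 = 212.8 / 252 = 84.4%.

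The SAP formula adds one day to each period. With 113 and 365 days the results are 289.4 / 365 = 79.3% and 293.3 / 365 = 80.4%, so neither classification changes.

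**Share of the long window after the endpoint**

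- After Week 16: 252 / 364 = 69.2%.
- After Week 24: 196 / 364 = 53.8%.

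Most of the information that decides membership under 6.2.1 therefore comes after the visit being analysed.

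**Which windows can be completed at the 24-week lock**

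| Window | Stated in | Complete at the 24-week lock? |
|---|---|---|
| Weeks 0–16 | 6.7 (PPS sentence and compliance plan) | Yes |
| Weeks 0–24 | 6.7 (compliance plan only) | Yes |
| Weeks 0–52 | 6.2.1; 6.15 by reference to Period 2 | No, for patients still in Period 2 |

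Patients enrolled early may have reached Week 52 by then, so the rule fails for the set as a whole rather than for every patient.

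**The case against.** **The PPS is secondary.** ITT is the main population, and the PPS enters neither the primary estimand nor the sample size. This stands, and it limits the weight of the point.

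**A workable rule already exists.** Section 6.7 gives a Week 16 exclusion that can be computed at the 24-week lock. Section 6.16 records that the 24-week analysis has been done, and the revision history places its description in SAP Version 2, whose PPS wording is not available. So the Week 16 window may have been the one used. This also stands, but the current text does not show it. A Week 16 rule alone would also leave the Week 24 PPS analyses with no compliance check between Weeks 16 and 24.

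**The Week 16 limit in 6.2.1 may cover all the criteria.** It follows the site GCP criterion, and the Week 52 limit is attached directly to compliance. A wider reading would not remove the conflict.

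**Section 6.15 may limit itself.** It excludes only for deviations that could affect efficacy analyses, and one made after Week 16 cannot affect a Week 16 result. The detail sits in the Trial Issue Management Plan, which is not among the documents. This is a fair reading, but 6.15 names only Period 2 and should state the visit.

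**Stronger readings that a reader might infer:**

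- *That 6.2.1 removes anyone noncompliant at any time in 52 weeks.* Compliance is cumulative. A patient fully compliant to Week 16 fails only if later compliance falls below 71.1%, and patient B shows that the longer window can also admit patients.
- *That the set both cannot be computed and conditions on later behaviour.* These are alternatives that depend on when it is built.
- *That the Week 16 PPS result changes between locks.* No section plans to rebuild that set at a later lock.

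**Conclusion.** The SAP is wrong as written. Sections 6.2.1 and 6.7 give different windows for the same exclusion, 6.15 follows the longer one, and the longer one does not fit analyses that all fall at Week 24 or earlier. The worked patients show that the windows can disagree in either direction. They rest on cumulative compliance at 3 tablets a day, no interruptions, and constant adherence within each segment.

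The consequence is modest: it concerns sensitivity analyses only. A reader might go on to infer a number of wrongly removed patients, an imbalance between arms or a bias favouring baricitinib. The documents support none of these. They give no rate of noncompliance or deviation after Week 16 and nothing by arm. The direction is also open: removing placebo nonresponders would raise the placebo response rate and work against baricitinib, while removing baricitinib nonresponders would do the opposite. The documents also do not show which window was applied at the 24-week lock.

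**What to change.** 1. **Section 6.2.1:** replace the Period 2, Week 52 limit on compliance with *through Week 16 for endpoints at or before Week 16, and through Week 24 for Week 24 endpoints*.
2. **Section 6.7:** make the same change to the sentence on PPS exclusion. If it stays at Week 16, the sections still disagree for the Week 24 endpoints.
3. **Section 6.15:** limit PPS-excluding deviations to those on or before the same visit (Week 16 or Week 24).
4. **Study report:** state which window was applied at the 24-week lock.

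The cost is SAP wording and two membership flags instead of one. Both compliance windows are already planned in Section 6.7 for the 24-week lock, so no new data are needed.

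One small downside remains. Endpoints at Weeks 1 to 4 would still be judged on compliance through Week 16, which runs past those visits. Matching each visit exactly is not possible for Week 1, because Protocol 7.6 first assesses tablet-return compliance at Visit 4 (Week 2).
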